6.1 Inclusion Criteria

In order to be enrolled in the study patients have to meet all the following criteria:

1. Diagnosis of severe or very severe aplastic anemia, defined by [29]:
 - At least two of the following:
 - Absolute neutrophil counts $<0.5 \times 10^9/L$ (severe) or $<0.2 \times 10^9/L$ (very severe)
 - Platelet counts $<20 \times 10^9/L$
 - Reticulocyte counts $<60 \times 10^9/L$
 - Hypocellular bone marrow ($<30\%$ cellularity), without evidences of fibrosis or malignant cells
2. Male or female age ≥ 15 years;¹
3. Written informed consent
4. Willing and able to comply with all of the requirements and visits in the protocol
5. Understands that they can be randomised to either treatment arm
6. Negative pregnancy test for women of child bearing age
7. Written acceptance to use contraception (hormonal or barrier method of birth control; abstinence) for the entire duration of study participation.

6.2 Exclusion Criteria

Patients with one or more of the following criteria cannot be included in the study:

1. Prior immunosuppressive therapy with ATG (horse or rabbit) or any other lymphocyte depleting agent (i.e., alemtuzumab)
2. Eligibility to a sibling allogeneic stem cell transplantation
3. Evidence of a myelodysplastic syndrome, defined by the presence of myelodysplastic features, excess of blasts or karyotypic abnormalities typical of MDS (according to revised WHO 2008 criteria) [30], as well as other primitive marrow disease. Patients with diagnosis of AA with cytogenetic abnormalities which are recurrent in MDS (according to revised WHO 2008 criteria) [30] should be included in this category, and are not eligible for the study; ***patients with del(20q), +8 and -Y are not included in this category, and thus are eligible for this study.*** The list of karyotypic abnormalities which qualifies for the diagnosis of MDS are listed in the Appendix 1.
4. History or clinical suspicion of constitutional aplastic anemia (i.e. Fanconi Anemia with positive DEB/MMC test or Dyskeratosis Congenita)
5. History of malignant tumors with active disease within 5 years from enrollment, and/or previous chemo-radiotherapy
6. Previous history of stem cell transplantation

¹Children in Care (CiC) are not excluded from this study, provided that the agency, organization, institution (or entity of the courts, the government or a government body) will work as legal guardian in signing the informed consent. CiC are defined as children who have been placed under the control or protection of an agency, organisation, institution or entity by the courts, the government or a government body, acting in accordance with powers conferred on them by law or regulation. The definition of CiC can include children cared for by foster parents or living in a care home or institution, provided that the arrangement falls within the definition above. The definition of a CiC does not include a child who is adopted or has an appointed legal guardian.

7. Treatment with cyclosporin A:
 - <4 weeks of cyclosporin A treatment before enrollment.
 - Wash out period of 2 weeks before enrollment.
8. CMV viremia, as defined by positive PCR (≥ 3.5 logarithm) or pp65 test (≥ 5 cells)
9. WHO performance status ≥ 3
10. Pregnant or breast feeding patients^{2,3}
11. Patients with end-stage hepatic, renal or cardiac failure, or any other life-threatening concurrent disease
12. Patients with HIV infection
13. Patients without social health care assistance
14. Participation in another clinical trial within 1 month before the start of this trial
15. Patients and/or female partners of male patients not using highly effective method of birth control i.e. intrauterine device (IUD), hormonal (oral pill, injection, implants), tubal ligation or partner's vasectomy
16. Patients with known hypersensitivity to any of the component medications

The presence of a Paroxysmal Nocturnal Hemoglobinuria clone **is not** an exclusion criterion.

Hepatitis-AA (HAA) syndrome [34] is not an exclusion criterion; similarly, the evidence of HBV or HCV infection is not an exclusion criterion *per se*, provided that there is no evidence of hepatic failure (see exclusion criterion #11)

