5.1 Primary Endpoint

Rate of Complete response (defined as Hb >10 g/dL, ANC > 1,000/ μ L and Plt >100,000 μ L) at 3 months since randomisation in untreated severe AA patients.

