5.2 Secondary Endpoints

1. Time to first hematological response (complete or partial) described by a cumulative incidence curve (see paragraph 9.6)
2. Time to best hematological response, described by a cumulative incidence curve (see paragraph 9.6)
3. Time to complete response (see paragraph 9.6)
4. Rates of hematological response (overall, complete, partial) at 6, 12, 18 and 24 months
5. Overall survival (OS) probability; OS is defined as time from randomisation to death, or last follow-up for patients alive
6. Event-free survival (EFS) probability; EFS is defined as time from randomisation to either relapse, death, treatment failure or clonal evolution (whichever occurs first), or last follow-up for patients alive in response
7. Cumulative incidence of relapse, from first hematological response (complete or partial) (see paragraph 9.6)
8. Cumulative incidence of clonal evolution (as defined below, see 9.5): AML, MDS or karyotypic abnormalities (see paragraph 9.6)
9. Cumulative incidence of PNH population occurrence and clinical hemolytic PNH occurrence (see paragraph 9.6)
10. Cumulative incidence of discontinuation of immunosuppressive therapy
11. Rate of CsA-independent hematological response at 24 months
12. Need for transfusions (packed red cell units and platelet units) and number of transfusions required from treatment.
13. Need for any supportive care, including hospitalization
14. Quality of life (as assessed by the validated EORTC QLQ-C30 questionnaire)(changes over time and differences between treatment arms)
15. Safety and tolerability of the investigational treatment, including SAE

6. Patient Selection and Withdrawal

All patients must meet all of the inclusion criteria and none of the exclusion criteria listed below. Protocol waivers are not acceptable in this trial.

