12.6 The selection of patients to be included in the analysis

All efficacy analyses will be based on the intention-to-treat principle, including all patients randomized and comparing groups based on the arm assigned at randomisation. In the unlikely case of patients found to be not eligible after randomisation or going off-study before receiving the treatment, these cases would be excluded, and secondary analyses will be performed to check the sensitivity of conclusions when these cases are included.

As specified in 9.6.1 and 12.3, the analysis of the primary endpoint will include all cases evaluable at 3 months, considering death before 3 months as a failure to achieve CR. Patients alive at 3 months and non-evaluable or withdrawals before 3 months will be excluded from the primary analysis, and sensitivity analyses will be performed to check the validity of

conclusions. The scenarios will be : i) all cases failures ; ii) all cases CR ; iii) all experimental arm cases failures, all control arm cases CR.

The safety analyses will be performed on the subpopulation of cases who started the treatment.

13. Data Management

The EBMT software in use at time of the beginning of the trial will be adopted for this study.

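### Exclusion 7 lists cyclosporin conditions whose literal effect conflicts with the untreated target population, the contraception criteria disagree, and Section 12.6 drops ineligible patients from the main efficacy analyses

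*Protocol*

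**What the plan says.** The opening of Protocol Section 6 sets a strict rule: "All patients must meet all of the inclusion criteria and none of the exclusion criteria listed below. Protocol waivers are not acceptable in this trial". Section 6.2 begins "Patients with one or more of the following criteria cannot be included in the study". Item 7 of that list, headed as treatment with cyclosporin A, has two bullets: "<4 weeks of cyclosporin A treatment before enrollment" and "Wash out period of 2 weeks before enrollment". The synopsis carries the same two bullets under its exclusion criteria. The primary endpoint in Section 5.1 is the complete response (CR) rate "at 3 months since randomisation in untreated severe AA patients".

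On contraception, inclusion 7 in Section 6.1 asks for "Written acceptance to use contraception (hormonal or barrier method of birth control; abstinence) for the entire duration of study participation", and footnote 2 to Section 6.2 repeats the same methods as adequate. Exclusion 15 bars patients, or female partners of male patients, who are "not using highly effective method of birth control i.e. intrauterine device (IUD), hormonal"; the list continues with tubal ligation and partner's vasectomy.

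On CMV viraemia, the synopsis excludes on a positive PCR or pp65 test without a threshold. Section 6.2 gives thresholds of 3.5 log and 5 cells.

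Sections 9.6.1 and 12.3 define the intention-to-treat (ITT) population as all randomised patients. Section 12.6 states the same principle for all efficacy analyses, but then says that "patients found to be not eligible after randomisation" would be excluded. It calls this case unlikely and plans secondary analyses that include these patients.

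**The concern.** An exclusion list works by disqualification: whatever stands in it keeps a patient out. The two cyclosporin bullets read like conditions under which prior cyclosporin would be tolerated, yet they stand where they disqualify. Cyclosporin is part of the treatment in both arms, so prior exposure bears directly on who counts as untreated. If the rule can be read in more than one direction, the population to which the result applies depends on how each site read it.

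The contraception texts raise a similar problem of consistent application. A patient can meet the inclusion criterion and still be barred by the exclusion criterion, and no waiver is available.

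The link to the analysis is Section 12.6. The trial is open label, and 12.6 names neither a blinded adjudication nor a time limit for the eligibility judgement. Where the criteria themselves are unclear, a judgement made after randomisation, with arm and possibly response known, decides who is in the main efficacy set. That is the selection that an all-randomised analysis is meant to prevent.

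**Working it through.** **Cyclosporin.** Two readings of exclusion 7 can be applied to the possible histories. 'Literal' means that each bullet disqualifies. 'Permissive' means that both bullets describe what is allowed.

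| Prior cyclosporin | Literal | Permissive |
|---|---|---|
| None | eligible | eligible |
| Under 4 weeks, 2-week wash-out done | barred (both bullets) | eligible |
| Under 4 weeks, no wash-out | barred (first bullet) | barred |
| 4 weeks or more, wash-out done | barred (second bullet) | barred |
| 4 weeks or more, no wash-out | eligible | barred |

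The readings disagree in the second and fifth rows, and they disagree in opposite directions. A mixed reading is also possible, because the second bullet does not say whether having or lacking the wash-out disqualifies. No other text settles it: the synopsis repeats the wording, and exclusion 1 names only ATG and other lymphocyte-depleting agents.

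**Contraception.** Each method is taken through both criteria.

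| Method | On the inclusion 7 list | Passes exclusion 15 |
|---|---|---|
| Hormonal | yes | yes |
| Barrier | yes | no |
| Abstinence | yes | no |
| IUD | no | yes |
| Tubal ligation or partner's vasectomy | no | yes |

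Only the first row passes both. Because all inclusion criteria and no exclusion criteria must be met, a barrier or abstinence user is literally ineligible although inclusion 7 and footnote 2 accept the method. An IUD or sterilisation user is literally outside inclusion 7 if its list is taken as closed.

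**Section 12.6.** Its first sentence puts all randomised patients in the efficacy analyses. Its second takes out those found ineligible and returns them in secondary analyses. The selected set is therefore the main one and the all-randomised set the secondary one, the reverse of what Sections 9.6.1 and 12.3 lead the reader to expect.

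**Sample size.** Inputs from Section 12.1: 7% versus 21%, two-sided alpha 0.05, power 80%. With pooled variance and mean rate 0.14:

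n = [1.960 × √(2 × 0.14 × 0.86) + 0.842 × √(0.07 × 0.93 + 0.21 × 0.79)]² / 0.14² = (0.962 + 0.405)² / 0.0196 ≈ 95.3, so 96 per arm.

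Dividing by 0.96 gives 100 per arm, 200 in total. The plan's figures reproduce, and nothing in the eligibility wording changes them. By the same method, power is 81.9% with 100 per arm, 80.3% with 96 and 77.7% with 90, so modest removals cost little power.

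**Why the order of the analyses matters.** The planning rates imply few responders, about 7 and 21 per 100. As a purely hypothetical example with an unstratified chi-square test:

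- 8/100 versus 17/100: pooled rate 0.125, z = 0.09 / √(0.125 × 0.875 × 2/100) = 1.92, p = 0.054.
- One control responder removed as ineligible, 7/99 versus 17/100: pooled rate 24/199 = 0.1206, z = 0.0993 / √(0.1206 × 0.8794 × (1/99 + 1/100)) = 2.15, p = 0.032.

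The planned test is a stratified Mantel-Haenszel test, so these p-values only illustrate sensitivity to a single exclusion.

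**The case against.** The strongest reply has four parts.

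First, no sensible site would bar a patient for having completed a wash-out, and patients never given cyclosporin are eligible on any reading. Prior ATG and lymphocyte-depleting treatment also remains excluded. This is fair, and it makes a strictly literal application unlikely. It does not supply the missing direction: the protocol states the cyclosporin rule nowhere else, and with waivers barred the written text is what a monitor or auditor will apply.

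Second, a reader might infer that sites cannot satisfy both contraception texts, or that their conflict lets the wrong patients in. Neither follows. A hormonal method meets both texts, and strict use of both keeps patients out. What stands is over-exclusion and the risk that sites apply different rules.

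Third, a reader might infer from 12.6 that patients can be kept or dropped at will. That leaves out half the paragraph: such cases are called unlikely, and analyses adding them back are planned, so the effect of a choice would be visible. The remaining point is narrower: the main analysis is not the all-randomised one.

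Fourth, a reader might infer that pre-treated entrants would undermine the 7% planning rate or bias the comparison. The protocol does not say whether the cited study admitted prior cyclosporin, and such entrants would be randomised 1:1 like the rest. The effect is on whom the result describes, and no planning figure is shown to be wrong.

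The CMV difference can be read as the full text giving detail that a synopsis left out. It is minor, though a low-positive patient is classified differently by the two texts.

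**Conclusion.** The point holds as a defect in operative wording joined to an analysis-set rule that should be turned round. Exclusion 7 as written conflicts with the untreated target population. That its bullets were meant as permitted conditions is a strong inference, but the protocol does not confirm it. Inclusion 7 and footnote 2 disagree with exclusion 15, with only hormonal methods common to both lists. Section 12.6 departs from the ITT population that the protocol defines, in an open-label trial.

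The size cannot be stated. The documents give no share of patients with prior cyclosporin, with a given contraceptive method, or later judged ineligible, and any percentage would be a guess. The 4% allowance (200 − 192 = 8 patients) is stated for non-evaluable patients, so it is not a measure of this problem. The sample size and power stand.

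**What to change.** 1. The sponsor should reconcile exclusion 7 so that each cyclosporin condition states explicitly whether it disqualifies or is permitted, identically in the synopsis and Section 6.2.
2. The sponsor should reconcile inclusion 7 and footnote 2 with exclusion 15, so that one list of methods applies throughout.
3. The sponsor should reconcile the CMV criterion between the synopsis and Section 6.2.

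Which cyclosporin, contraception or CMV rule applies is a clinical decision for the sponsor, and this review does not choose one.

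4. In Section 12.6, keep randomised patients found ineligible in the primary ITT analysis, in the arm assigned, and make the analysis without them the sensitivity analysis.

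The cost is amendment wording, including the matching text in the synopsis. No extra data are needed, since the planned secondary analyses already require outcomes for these patients, and the sample size does not change.

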6.3 Early withdrawal of a patient / patient drop-out from the trial treatment

The site investigator should withdraw a patient from the trial treatment whenever continued participation is no longer in the patient's best interests. In particular, change of protocol treatment is expected in case of treatment failure (as defined in paragraph 9.4) for those patients who are eligible for second-line treatment (i.e., transplantation or second course of immunosuppression).

In addition reasons for discontinuing treatment may include:

1. the occurrence of a serious adverse event:
2. unrelated medical illness or clinical conditions representing a potential risk - at judge of the investigator, including pregnancy.
3. significant protocol violation or non-compliance (including unmotivated refusal by the subject for prescribe study procedures and post-treatment follow up).
4. a patient's own request to end treatment.

²Eltrombopag was not teratogenic when studied in pregnant rats and rabbits but caused a low incidence of cervical ribs (a fetal variation) and reduced fetal body weight at doses that were maternally toxic. There are no adequate and well-controlled studies of eltrombopag in pregnant women. The effect of eltrombopag on human pregnancy is unknown. Therefore women of childbearing potential must agree to use adequate contraception prior to (hormonal or barrier method of birth control; abstinence) and for the duration of study participation. If a woman becomes pregnant or suspects she is pregnant while on study, her treating physician should be informed immediately.

³ATGAM was not teratogenic when studied in rats or monkeys at a dose up to 20 mg/kg. However, 20 mg/kg/day ATGAM for 16 days during organogenesis in cynomolgus monkeys was fetotoxic. No fetal or maternal toxicity was seen with 10 mg/kg/day ATGAM administered for 16 days during organogenesis. There are no adequate and well-controlled studies in pregnant women. It is also not known whether ATGAM can cause fetal harm when administered to a pregnant woman or can affect reproduction capacity.

If a patient is withdrawn from treatment for any reason, he or she remains in the trial and is followed through the regular follow ups for the normal duration of the described participation as per protocol, unless the patient specifically withdraws consent from the trial.

6.4 Early withdrawal of a patient / patient drop-out from the trial

According with the current revision of the Declaration of Helsinki and other applicable regulations, a subject has the right to withdraw from the study at any time and for any reason without prejudice to his future medical care by the physician. A patient may decide at any time that they no longer wish to continue in the trial without their medical care being affected and without having to provide a reason for discontinuation. In this event, the investigator should try and establish the reason why the patient no longer wishes to participate in the trial and record the reasons in the CRF as well as in the patient's notes; the patient is not obliged to supply this.

Any patient who is withdrawn from the trial at any time for any reason before the last follow up visit is considered an early withdrawal. A complete set of data including the reason for withdrawal should be collected for every early withdrawal patient up to the time of withdrawal from the trial. **Regardless of the reasons for discontinuing in the trial, patients should be followed up for a minimum of 90 days after the last dose of IMPs in order to obtain safety data.**

6.5 Patients lost to follow-up

Every effort should be made to obtain information on patients who do not attend a scheduled appointment, to obtain at least minimal efficacy and safety data (including Serious Adverse Events). A patient will be considered lost to follow-up if they miss 3 consecutive visits and cannot be contacted by the site on 3 separate, consecutive attempts (these attempts must be documented on patient's notes).

6.6 Termination of an investigator's participation in the trial

The investigator may terminate his or her site's participation in the trial. If this occurs they must provide a written statement of the reasons for terminating participation and should provide the EBMT Clinical Trials Office (CTO) with all available and up-to-date trial data.

The trial steering committee may also decide to terminate participation of an investigator or trial site for the following reasons:

- Breach of agreement
- Serious non-compliance with International Conference on Harmonisation for Good Clinical Practice (ICH-GCP) standards (see section 14)
- Insufficient patient recruitment

For composition of the Trial Steering Committee the please refer to appendix 10.

If a participating site closes, or is closed, prior to termination of the whole trial, the EBMT requires that data from patients already entered into the trial will be reported as per protocol,

unless the patient(s) have withdrawn consent for data collection. In addition, the treatment of the patients already included in the trial will be discussed and agreed with the EBMT.

The end of the trial is defined in section 11.

7. Patient Treatment and Visit Schedule

7.1 Patient Registration/ Randomisation

To register a patient in the trial the site must complete the RACE registration form and fax this to the EBMT CTO. The registration form must be signed by the PI or Co-Investigator listed on the staff delegation log.

On receipt of the patient registration form the patient data will be entered in the Clinical Trials Management System (CTMS) and the patient will be assigned a unique patient number. The EBMT CTO will send a registration confirmation to the site.

A patient will be considered enrolled in the study when registration of the patient is confirmed by the EBMT Clinical Trials Office.

Randomisation will take place on the day or day before hATG is started. The time between registration and randomisation should be no longer than 7 days.

To randomise a patient the site must complete the RACE randomisation form and fax this to the EBMT CTO. The randomisation form must be signed by the PI or Co-Investigator listed on the staff delegation log.

The patient data will be entered in the CTMS and the patient will be randomised to either the standard or the investigational arm. The EBMT CTO will send the randomisation result to the site.

Randomisation ratio will be 1:1. Randomisation will follow a stratified variable length block design. Stratification will be done according to patient's age and disease severity to ensure homogeneity between treatment arms, according to the following subgroups:

Disease severity:

- Severe aplastic anemia (SAA)
- Very severe aplastic anemia (VSAA: SAA plus ANC <200/ μ L)

Age:

- ≥ 15 and <40 year old
- ≥ 40 year old

A stratification by centre will be considered as an additional balancing factor for randomisation, based on the center size (i.e. the number of patients expected to be entered into a center in this trial). A center is classified as "large" if the anticipated number of patients to be entered exceeds 20. Otherwise the center is classified as "small". All centers classified as small will be treated as one single stratum; all large centers have their own stratum. Hence randomisation will be balanced within each large center on disease severity and age; and likewise within the pool of all small centers.

Patient registration and randomisation forms will be processed Monday to Friday from 09.00 -17.00 CET.

- Forms received after 17.00 will be processed the next day.
- Forms received over the weekend will be processed the following Monday morning.

